#### **Aim 2**

Descriptive statistics will be used to examine treatment related costs and we will organize qualitative data thematically using NVivo software.

#### **Aim 3**

The primary variable is in-home pill count percent established on each monthly visits or virtual visits. Secondary variables are MPR, PDC, SRHI automaticity SRHI total score, Symptoms and SOFAS scores. We will examine within group change and effect sizes using a likelihood-based population-averaged (marginal) generalized linear regression model with repeated measures as implemented in the SAS GLIMMIX procedure specifying binomial (proportions) or normal (scales) as appropriate. A-likelihood based regression model with repeated measures makes the best use if all the information including cases with incomplete or missing data. The primary hypothesis tests planned contrasts at the final assessment of within-arm change and the difference between arms.

We will examine trajectories for 4 groups; the 2 groups with a preference (for either R-CAT or CAT) that were self-selected the 2 groups who did not indicated a preference and were randomized to either CAT or R-CAT. We will examine differences in baseline characteristics between the two groups with preferences as these differences may be related to outcome in the self-selected samples.

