**Medication Adherence (baseline and once monthly until 6 months or study completion)** - based upon our own work and recent publications, medication adherence will be assessed using unannounced in-home pill counts conducted every other month (months 0, 2, 4, 6) with video counts done in the intervening months (1, 3, 5). We will also have electronic claims data provided by the MCO. The primary measure will be in-home pill counts due to evidence that this measure is more sensitive to treatment changes. An initial visit prior to randomization [or initiation of chosen intervention] is conducted to count and bag all old pills, identify current bottles, count current pills in the bottles and any medication containers used by the individual. A box is set up with a sign to remind participants not to throw out empty bottles. Counts are conducted monthly in an attempt to capture all prescription refills and medication changes. Adherence percent is calculated as the number of pills missing and presumed taken/ the number of pills prescribed for the time period X100. Percentage of all mental health medications and a percentage for all medications will be calculated. The latter being the primary measure. We used these procedures in two R01's previously. We will also obtain prescription refill data from MCO records. We will calculate Medication Possession Ratio (MPR) and Proportion of Days Covered (PDC) as secondary measures of adherence. MPR is calculated as the day's supply for all fills of a medication in the time period divided by the number of days in the time period X 100. PDC is calculated by the number of days "covered" divided by the number of days in the time period X 100. PDC is less commonly used but is endorsed by the Pharmacy Quality Alliance and is now incorporated into Medicaid and Medicare services in their plan ratings. Moreover, for individuals on multiple medications, PDC better characterizes overall adherence. (20-40 minutes depending upon person's organization and number of medications).

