## 10. Study Intervention Additional Details

### 10.1. Measures to Minimize Bias: Randomization and Blinding

This section should contain a description of randomization and blinding procedures (if applicable to the study design). It should include a description or a table that describes how study participants will be assigned to study groups, without being so specific that blinding or randomization might be compromised. Plans for the maintenance of trial randomization codes and appropriate blinding for the study should be discussed. The timing and procedures for planned and unplanned breaking of randomization codes should be included. Include a statement regarding when unblinding may occur and who may unblind. Provide the criteria for breaking the study blind or participant code. Discuss the circumstances in which the blind would be broken for an individual or for all participants (e.g., for serious adverse events (SAEs)). Indicate to whom the intentional and unintentional breaking of the blind should be reported.

Those with no preference for CAT or R-CAT will be Randomized, 1:1 done by statistician who has no patient contact through a random allocation program. If blinds are broken accidentally, new raters can be assigned, but blinds are kept by having raters and pill counters unaware of treatment group or study design.

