### 12.2. Sample Size Determination

Include number of participants to recruit, screen, and enroll to have adequate power to test the key hypotheses for the study. Provide all information needed to validate your calculations and judge the feasibility of enrolling and following the necessary number of participants.

This is a pilot study and not powered for testing efficacy. Given that, we examined power for proportions using PASS (Aims 1 and 2). We will approach a minimum of 200 individuals to examine the acceptance rates of an initial offer of CAT versus R-CAT. We will be able to detect a 20% difference in proportions in acceptance with a power greater than .80; two-tailed alpha =0.05. We don't expect dropout rates to vary greatly between the 2 treatments but with 100 individuals and 50 in each of 2 treatment groups we will be able to detect a difference in drop out of at least 10% versus 30% at a power of .80; alpha=0.05. A smaller difference in dropout across 6 months would not be likely to impact decisions about which treatment to adopt and is not important to detect. Aim 3 examines differences from baseline within 4 groups (those with a preference for CAT; those with a preference for R-RCAT; those with no preference randomized to CAT and those with no preference randomized to R-CAT). With 25 per group for the randomized samples within each treatment SAS Power indicates that the smallest detectable effect would be for pill count adherence going from 70% to 85%. We would have power of .80 to detect difference of about 25% in pill count adherence proportions that that correlate .48 with probabilities of adherence from 60-85% in with a one tailed test at alpha of .05. <http://statulator.com/SampleSize/ss2PP.html>. This was verified using a simulation using 5000 replications. A one-tailed test is used as we are not interested in whether the intervention makes adherence worse.

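### Aim 3 does not specify baseline adjustment for the randomised CAT versus R-CAT contrast, which leaves avoidable imprecision at about 25 per arm

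*Combined protocol and SAP*

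**What the plan says.** Section 12.4, Aim 3, plans a marginal, likelihood-based repeated-measures model in SAS GLIMMIX, binomial for proportions and normal for scales. On the tests it says: "The primary hypothesis tests planned contrasts at the final assessment of within-arm change and the difference between arms". On the outcome: "The primary variable is in-home pill count percent established on each monthly visits or virtual visits". The secondary variables are MPR, PDC, SRHI automaticity (SRBAI), SRHI total, symptoms (BPRS) and SOFAS. Trajectories are examined in four groups: two self-selected and two randomised. Baseline comes up only in a comparison of characteristics between the two self-selected groups. No fixed effects, covariates or constraints on baseline means are listed.

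Section 10.1 states: "Those with no preference for CAT or R-CAT will be Randomized, 1:1". Section 12.2 plans on 25 per randomised group.

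Section 8.6, Part 2, collects BPRS, SRHI and SOFAS at baseline and months 2, 4 and 6. It places an initial pill-counting visit before randomisation. Inclusion criterion 6 in section 6.2 relies on refill-based MPR over the past four quarters, so pre-treatment claims data exist.

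**The concern.** Members without a preference are randomised, so the true baseline means of their two arms are equal. A longitudinal model that gives each group its own free baseline mean makes no use of this. With complete data, its month-6 arm contrast is then a difference in final means or a difference in mean change. Having baseline among the repeated measures does not by itself amount to adjustment. That requires either a baseline mean held common across the randomised arms or baseline entered as a covariate.

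Sections 3 and 12.1 hypothesise that change is similar in CAT and R-CAT, and section 12.4 makes the arm difference part of the primary hypothesis. With about 25 per arm, interval width largely decides what can be said about similarity. Leaving the contrast open also lets the choice among three estimators be made after the data are seen.

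**Working it through.** **Inputs.** From section 12.2: 25 per randomised group; adherence from 60% to 85%; one-tailed alpha .05; power .80; and "pill count adherence proportions that that correlate .48". Assumed here: a linear model, equal variances at baseline and month 6, one baseline value and one final value.

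**1. The plan's own figure (within-group, paired proportions).**
- Both adherent: .60 × .85 + .48 × √(.24 × .1275) = .594.
- Discordant cells: .600 − .594 = .006 and .850 − .594 = .256. Their sum is D = .262, and the difference is d = .25.
- n = [1.645√D + 0.842√(D − d²)]² / d² = 23.7, so 24. Power at 25 is .82.

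The stated power of .80 at 25 is reproduced, so .48 is the within-person correlation in that calculation.

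**2. Variance of the between-arm contrast, relative to final level.**
- Final level only: 1.
- Difference in change: 2(1 − r). At .48 this is 1.04, slightly worse than ignoring baseline.
- Baseline-adjusted: 1 − r². At .48 this is .77.
- Adjusted against change: (1 − r²) / [2(1 − r)] = (1 + r)/2. At .48 this is .74.

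**3. Large-sample variance cut over a range of r.**

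| r | against final level | against change |
|---|---|---|
| .3 | 9% | 35% |
| .48 | 23% | 26% |
| .6 | 36% | 20% |
| .7 | 49% | 15% |

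**4. Cost of estimating the slope at 25 per arm.** The factor is 1 + 1/(2 × 25 − 4) = 1.022. At r = .48 the ratios become .7696 × 1.022 = .786 and .74 × 1.022 = .756, so cuts of 21% and 24%. A simulation of 40,000 trials gave 22% and 24%. Against final level, adjustment pays only if r² exceeds 1/47 = .021, that is r above about .15.

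**5. What this means at r = .48.**
- Large-sample equivalent size: 25/.7696 = 32.5 or 25/.74 = 33.8 per arm.
- Detectable difference (two-sided .05, power .80): 2.80 × √(2/25) = 0.79 SD for final level, 2.80 × √(2 × 1.04/25) = 0.81 SD for change, and 2.80 × √(2 × .7696/25) = 0.70 SD adjusted.

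**6. Unequal variances.** Treating adherence as binary at 60% and 85% gives variances of .24 and .1275. In simulation, the cut against final level is still 22%; against change it is about 50%.

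**7. Is there a baseline value to adjust for?** BPRS, SRHI/SRBAI and SOFAS: yes. MPR: yes, from claims; PDC should be computable from the same records. Pill-count percent: uncertain. Section 8.6 divides pills presumed taken by pills prescribed over a period. The initial visit bags old pills and counts current ones, which appears to open the first period, and no earlier count is described.

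**The case against.** **The plan is silent; it does not exclude adjustment.** Correct. A reader might infer that the analysis will not adjust, but section 12.4 supports only the statement that adjustment is not specified.

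**The .48 does not travel.** It belongs to paired pill-count proportions in a within-group power calculation. No correlation is given for BPRS, SRBAI, SRHI, SOFAS, MPR or PDC. A reader might infer a gain of about a quarter on the primary outcome or on the scales. The documents support neither. If claims PDC or MPR has to stand in as the covariate for pill count, its correlation with month-6 pill count appears nowhere, and selection on low MPR in section 6.2 could weaken it. At r = .2 the cut against final level is 4% before the slope is paid for.

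**The model for proportions is binomial.** The link is not named. With a logit link, a baseline covariate turns the arm effect into a conditional odds ratio, while the plan asks for a population-averaged one. This stands, and the fix has to deal with it.

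**It is a pilot.** Section 12.2 disclaims power for efficacy, and sections 4 and 12.2 treat Aim 3 mainly as within-group change. Even the adjusted detectable difference, 0.70 SD at r = .48, is large. This limits the importance of the point without removing it, since section 12.4 still tests the arm difference.

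**Other randomised comparisons exist.** A reader might take this contrast to be the only unconfounded one in the trial. It is not: Part 1 randomises which treatment is described first, and section 12.4, Aim 1, compares dropout and satisfaction separately in the randomised groups.

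**Conclusion.** The point holds as a recommendation on precision. Section 12.4, Aim 3, specifies no baseline adjustment for the randomised pair, and the contrast it describes is less precise than it could be with data already planned.

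The size is conditional on r: the large-sample variance cut runs from 9% to 49% against final level, and from 35% down to 15% against change, as r goes from .3 to .7. At the only correlation the documents give, it is about 21–22% or 24% after the small-sample cost. These figures rest on a linear, equal-variance model and on 25 per arm actually stating no preference. For pill-count percent the size cannot be stated from the documents.

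The unadjusted randomised contrast is unbiased, so nothing here makes it invalid. Nor does the point concern confounding in the self-selected groups, which a common baseline mean would not cure and should not be applied to.

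**What to change.** In section 12.4, Aim 3, add for the members randomised between CAT and R-CAT only:

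- **BPRS, SRBAI, SRHI, SOFAS:** one common baseline mean across the two arms (constrained longitudinal model), or baseline as a covariate with the follow-up visits as responses.
- **MPR and PDC:** adjust for the pre-treatment claims value of the same measure.
- **Pill-count percent:** adjust for a pre-treatment value if one exists, otherwise for pre-treatment PDC or MPR. State which, and say in section 8.6 whether the initial visit yields a percent.
- **Any binomial model with a logit link:** report a standardised (marginal) arm difference so that the estimand stays population-averaged.

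Keep separate baseline means for the self-selected groups. State whether the arm contrast is a difference in change or in level, and that it is estimated in the randomised pair.

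The cost is a short addition to the model text, one slope or constraint per outcome at 25 per arm, and a standardisation step for binomial outcomes. No new assessments are needed; the pre-treatment refill records must be kept in the analysis data.

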We will use components of the Reach, Effectiveness, Adoption, Implementation, Maintenance (RE-AIM) framework to compare Cognitive Adaptation Training (CAT) to Remotely delivered Cognitive Adaptation Training (R-CAT) 1-9 within a managed care organization (MCO), targeting members with serious mental illness (SMI) needing assistance with the regular taking of medication. In Part 1 of the research, **to assess both pre-implementation parameters and potential effectiveness, we will survey approximately 200-400 MCO members identified as having difficulty with medication follow through. CAT or R-CAT will be described in a randomized way and asked about acceptance, participants will then be told about the other intervention and asked about acceptance. Participants will then rate a series of statements covering dimensions of these treatments on the extent to which they agree/disagree with each statement. After the survey, participants will be offered the opportunity to participate in a research study examining CAT and R-CAT. Those who prefer one treatment over the other will get that**

treatment and those with no preference will be randomized 1:1 to CAT or R-CAT. This procedure will be followed and then altered as needed until 50 have accepted or been randomized to each group. Treatment will be offered for 6 months. In R-CAT interventions will be delivered primarily by remote and electronic means. Medication follow-through will be assessed using monthly unannounced pill counts. Automaticity (Habit formation), treatment satisfaction, barriers and facilitators to treatment and psychiatric symptoms will be assessed at baseline and every other month. Costs of providing CAT and R-CAT will be recorded including driving time, assisting with technology use, shipping, mileage, time in direct contact with member, time preparing for visits, and supports provided. Outcomes will be evaluated using within group repeated measures analyses. In sum, we are proposing to assess acceptability, feasibility, treatment satisfaction, pre-implementation parameters such as caseloads and costs, and preliminary efficacy of R-CAT compared to traditional home-delivered CAT.

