### 12.4. Statistical Analyses

Include analysis of primary efficacy endpoints, secondary endpoints, safety analyses, and any planned interim analyses

#### Aim 1

We will use X analyses to examine differences in proportions. We are interested in the rate of acceptance of CAT versus R-CAT when only one treatment is offered as an ecologically valid way of looking at acceptance rates in a real-world situation. In addition, we will examine acceptance of the 2nd treatment when the first is declined. We will also look at overall acceptance once both treatment options are explained (CAT, R-CAT, Neither) and whether the order in which the treatments were offered impacts acceptance. Finally, after both treatment options are presented, we will examine stated preference given an offer of both treatments (CAT, R-CAT, no preference, no

treatment desired). We will compare dropout by treatment group (CAT/R-CAT) using X2 analyses examining randomized and self-selected groups both combined and separated.

We will compare treatment satisfaction between groups using t-tests comparing CAT versus R-CAT examining randomized and self-selected groups both combined and separated.

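### Self-selected and combined CAT versus R-CAT comparisons are left unadjusted, although the plan itself says baseline differences between the preference groups may matter for outcome

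*Combined protocol and SAP*

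**What the plan says.** Treatment assignment is mixed. Under section 4, people who prefer one treatment get it, and the sentence continues: "treatment and those with no preference will be randomized 1:1 to CAT or R-CAT". Section 12.2 counts 50 per treatment and 25 per randomised group.

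Section 12.4, Aim 1, then plans two between-treatment tests:
- Dropout: "We will compare dropout by treatment group (CAT/R-CAT) using X2 analyses examining randomized and self-selected groups both combined and separated".
- Satisfaction: "We will compare treatment satisfaction between groups using t-tests comparing CAT versus R-CAT examining randomized and self-selected groups both combined and separated".

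Section 12.4, Aim 3, uses a "likelihood-based population-averaged (marginal) generalized linear regression model with repeated measures as implemented in the SAS GLIMMIX procedure" and follows four groups, two self-selected and two randomised. It adds: "The primary hypothesis tests planned contrasts at the final assessment of within-arm change and the difference between arms". It names no covariates and does not say whether an arm here means the randomised participants, the self-selected ones, or both.

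On baseline imbalance it says only: "We will examine differences in baseline characteristics between the two groups with preferences as these differences may be related to outcome". Neither the protocol nor the SAP section mentions covariate adjustment, propensity methods, or stratifying the combined tests by how treatment was assigned.

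**The concern.** People who choose home visits and people who choose remote support may differ in prior adherence, symptoms, diagnosis or age. The plan recognises that such differences could bear on outcome, yet it stops at looking for them. Any imbalance passes straight into the self-selected comparison and, diluted, into the combined one.

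The direction is unknown. Section 12.1 expects changes of similar size in the two treatments, so confounding could create a difference where none exists or hide one that does. Section 12.2 ties the dropout comparison to decisions about which treatment to adopt, and section 3 says the pilot data are to inform future trials and community uptake. Covariates chosen after the data have been seen would carry less weight than covariates named now.

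**Working it through.** **1. The plan's own figure.** Section 12.2 gives power .80 for dropout of 10% versus 30%, 50 per arm, alpha 0.05 (sidedness not stated there). With pooled rate 0.20, the null SE is √(2 × 0.20 × 0.80 / 50) = 0.080 and the alternative SE is √(0.09/50 + 0.21/50) = 0.0775.
- One-sided: (0.20 − 1.645 × 0.080) / 0.0775 = 0.88, power 0.81.
- Two-sided: (0.20 − 1.96 × 0.080) / 0.0775 = 0.56, power 0.71 (0.73 by exact enumeration of the chi-square test).

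The figure reproduces one-sided only, which is a separate matter. What counts here is the expected number of events: 50 × 0.10 + 50 × 0.30 = 20.

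**2. How a baseline gap reaches a continuous outcome (illustration).** Inputs:
- Correlation .48, given in section 12.2 for paired pill-count adherence.
- 25 per self-selected group, inferred as 50 − 25. The documents do not state it.
- Baseline gap d between self-selected groups of 0.2, 0.5 or 0.8 SD: assumed.
- Equal SDs at both times and no true treatment effect: assumed.

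Final-value bias is .48 × d in the self-selected groups and half that when they make up half of the combined sample. Bias in change from baseline is (.48 − 1) × d = −.52 × d. A simulation with 4,000 replicates and two-sided 5% tests gave:

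| Gap (SD) | Self-selected, final value: bias; false positives | Combined, final value: bias; false positives | Self-selected, change: bias; false positives |
|---|---|---|---|
| 0.2 | 0.10; 7% | 0.05; 6% | −0.11; 7% |
| 0.5 | 0.24; 13% | 0.12; 9% | −0.26; 14% |
| 0.8 | 0.38; 27% | 0.19; 15% | −0.41; 28% |

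Adjusting for the baseline covariate gave bias near 0 and about 5% false positives throughout. That result is built in, because the simulated confounder is exactly the covariate adjusted for.

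**3. The same for dropout (illustration).** Assume a baseline risk factor with 30% dropout when present and 10% when absent.
- Present in 40% versus 60% of the two self-selected groups: expected dropout is 10 + 20 × 0.4 = 18% versus 10 + 20 × 0.6 = 22%. The chi-square test at 25 versus 25 rejects about 7% of the time.
- Present in 30% versus 70%: 16% versus 24%, rejecting about 11%.
- Combined with randomised participants at 20%, the rates become 19% versus 21% and 18% versus 22%, rejecting about 6% and 8% at 50 versus 50.

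**4. Does examining baseline differences protect?** If it means a test, a 0.5 SD gap at 25 versus 25 has noncentrality 0.5 × √(25/2) = 1.77 on 48 df and power of about 41%. A gap of that size would be missed more often than found.

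**5. How much adjustment dropout can carry.** Arm, assignment factor, MPR, BPRS, age and diagnosis (2–3 terms) make 7–8 parameters, or 20/8 = 2.5 to 20/7 = 2.9 events each. Arm, assignment factor, MPR and two-level diagnosis make 4 parameters, or 5 events each. In the self-selected groups alone, 25 × 0.10 + 25 × 0.30 = 10 events over 3 parameters is 3.3 each.

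**The case against.** The strongest reply is that the plan already keeps the groups apart. Section 12.2 frames Aim 3 as differences from baseline within four groups, section 4 speaks of within-group analyses, and 12.4 reports the Aim 1 comparisons separately as well as pooled. An unconfounded randomised comparison is therefore available throughout. This stands, and it limits the point to the self-selected and combined contrasts. It does not clear them: pooling is explicit for dropout and satisfaction, and the Aim 3 arm contrast is undefined.

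A second reply is that a repeated-measures model already uses the baseline value of the outcome. That is true of Aim 3, but a change contrast does not remove the problem when the gap partly regresses, as in step 2. It would do so if the gap were permanent, and the documents do not say which applies. The reply does not reach the dropout chi-square or the satisfaction t-test, which carry no covariates.

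A third reply is that this is a pilot not powered for efficacy. That lowers the consequence and leaves the comparisons as they are.

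A reader might also infer a bias in adherence points. A 10-point gap would give 10 × .48 = 4.8 points, but the documents give no gap, the sum needs equal SDs and a final-value contrast, and a change contrast gives 10 × (.48 − 1) = −5.2. Nor do the documents support a promised precision gain such as 1 − .48² = 0.77 of the variance. The .48 belongs to repeated pill counts, and no correlation is given between follow-up pill count and MPR, diagnosis, BPRS or age.

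**Conclusion.** The point holds in limited form and should be acted on. The plan names a possible confounder and then makes self-selected and combined comparisons of dropout and satisfaction without using it. It tests an Aim 3 arm difference with no covariates and no statement about pooling.

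The size is illustrative: false-positive rates of about 7–27% (self-selected) and 6–15% (combined) on final values. These rest on an assumed 0.2–0.8 SD gap, the adherence correlation of .48 applied more widely, and an inferred 25 per self-selected group. The actual gap could be nil.

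Three stronger readings are not supported:
- That Aim 3 is stated to pool randomised and self-selected participants. The text is ambiguous.
- That the plan says baseline differences drive outcome. It says they may be related to it.
- That no valid between-treatment comparison exists. The randomised one is valid, though it speaks for people without a preference.

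**What to change.** Revise section 12.4 as follows.

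1. State that the contrast among randomised, no-preference participants is the lead between-arm comparison. Report self-selected and combined contrasts second, labelled non-randomised and adjusted for measured confounders only. Say which participants make up each arm in the Aim 3 contrast.
2. In the Aim 3 between-arm contrasts, prespecify a small fixed covariate set already available: pre-enrolment MPR and diagnosis (both used for eligibility), baseline BPRS, and age. Add a randomised/self-selected factor to any combined contrast.
3. For satisfaction, replace the t-test in the self-selected and combined samples with a linear model using the same covariates, plus that factor when combined.
4. For dropout, prespecify a reduced logistic model: arm, MPR, diagnosis collapsed to two levels, and the randomised/self-selected factor when combined. Name a penalised fit, and the condition for using it, in advance, so that the model does not depend on how many events occur.
5. Claim no specific gain in precision.

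The cost is SAP wording and a few degrees of freedom; no new data are needed. Unmeasured confounding stays in the non-randomised contrasts, and the text should say so.
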